Labor and Delivery Implant Insertion (LADII)

[name]
[REDACTED], MPH
[name], MS
Stanford University

Phone: [REDACTED]
Email: [REDACTED]

Project Summary:

Investigating the timing to lactogenesis stage II (defined as the initiation of copious milk secretion) in women who obtain the contraceptive implant in delivery room versus the postpartum ward will add important data to the literature. If insertion in this time period is found to be without negative effects on breastfeeding the study findings would facilitate earlier insertion of the contraceptive implant, in the delivery room. Gurtcheff et al. recently analyzed time to lactogenesis in women initiating the contraceptive implant prior to medical discharge following delivery and 4-8 week postpartum and found no difference. In the proposed study, we seek to add to the literature by investigating immediate post-delivery insertion in the delivery room of the contraceptive implant versus insertion prior to medical discharge in the postpartum ward.

We propose a non-inferiority randomized controlled trial comparing time to lactogenesis stage II in healthy women with immediate insertion (0-2 hours following delivery) of the contraceptive implant in the delivery room versus in women with insertion of the contraceptive implant following delivery in the postpartum room and prior to medical discharge (24-48 hours following delivery). We hypothesize there will be no significant difference in time to lactogenesis with immediate delivery room (0-2 hours following delivery) vs. postpartum ward insertion (24-48 hours). In addition, we plan to follow women postpartum to evaluate breastfeeding continuation and exclusivity, discontinuation of the implant and any adverse events.

Description of the Project:

1.1 Rationale:

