Patients will be counseled about risks and benefits of contraceptive options and will be counseled appropriately regarding risks and benefits of subdermal contraception implant, as well as the unknown effects of early progestin administration on breastfeeding. Patients will not be eligible for the study unless they have been consented for a postpartum contraceptive implant prior active labor. If the patients meet inclusion criteria they will be invited to participate in the study and consent will be obtained. When a study patient is admitted to L&D, they will be met by research personnel and be randomized to one of the two arms. Participants will be randomized through block randomization—allocation will be sealed in an opaque envelope. The patient, provider, and research staff will be aware of arm allocation, this is not a blinded study. At this time, baseline data will be collected on patient age, gravidity, parity, breastfeeding experience on REDCap with a designated Ipad.

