Participants will receive brief telephone follow-up, including an interview at 4-8 weeks, 3, 6, and 12 months from date of delivery.

Criteria for discontinuation:

Participants who experience complications during labor and delivery or whose infants have medical problems will be discontinued. Patients who change their mind about contraceptive implant use will be discontinued. Intention to treat analysis will be employed.

Lab and other investigations:

Not applicable.

Data Management

Data will be collected on REDCap software, will be coded, monitored, and verified.

Data Analysis

SPSS version 23 will be used for data analysis.

Number of subjects and statistical power:

Based on previous reports of women with uncomplicated vaginal deliveries, mean time to lactogenesis stage II is 54 hours with a standard deviation of 12 hours. [21] If there is truly no difference between immediate insertion and delayed insertion of the contraceptive implant on time to lactogenesis stage II, then 68 patients are required to be 80% sure that the lower limit of a one-sided 95% confidence interval (or equivalently a 90% two-sided confidence interval) will be above the non-inferiority limit of a mean difference of 12 hours (alpha 5%; SD 18). Sealedenvelope.com was used to calculate

sample size based on these parameters. A non-inferiority margin of 12 additional hours is chosen to be relevant because common medical interventions like epidural anesthesia, cesarean section, labor induction, have been to delay stage II lactogenesis by up to 12 hours. [22] To account for potential participant dropout, 82 participants will be recruited.

Study limitations:

This is not a blinded study; appropriate blinding would require the use of placebo implants and additional procedures. We do not anticipate our inability to blind participants and providers to impact our primary outcome of time to lactogenesis stage II.

Our recruitment will be limited to the Stanford Obstetrics and Gynecology service. Thus internal validity will not be a concern, but this clinic's population is not representative of the diversity of the female population in the United States or of women giving birth in the United States.

Based on this study's inclusion and exclusion criteria, results cannot be extrapolated to women with some medical conditions, complications, during labor and delivery, or who have infants with medical problems.

Duration of project:

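### The only success criterion puts the wrong confidence limit on the wrong side of the 12-hour margin, the direction of the difference is never defined, and the hypotheses do not refer to the margin

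*Combined protocol and SAP*

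**What the plan says.** The success criterion appears once, in Number of subjects and statistical power. Assuming no true difference between the arms, 68 patients are to give 80% assurance that "the lower limit of a one-sided 95% confidence interval (or equivalently a 90% two-sided confidence interval) will be above the non-inferiority limit of" a 12-hour mean difference, with alpha 5% and SD 18. The 12 hours carries no sign.

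The same section fixes the direction of harm: "A non-inferiority margin of 12 additional hours is chosen to be relevant", with the reason that common peripartum interventions delay lactogenesis by up to that amount. It cites a literature value, "mean time to lactogenesis stage II is 54 hours with a standard deviation of 12 hours", but uses SD 18 in the calculation.

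Data Analysis consists of one sentence: "SPSS version 23 will be used for data analysis". It gives no contrast, test, interval or success rule.

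Project Summary and Objectives and hypotheses both call the trial non-inferiority. The hypothesis in Project Summary begins "We hypothesize there will be no significant difference in time to lactogenesis with immediate delivery room", and the one in Objectives and hypotheses is worded almost identically. The objective asks whether the times differ, and the section on expected outcomes anticipates that they will not. None of these statements mentions the 12-hour margin.

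**The concern.** To rule out a delay of 12 h or more, the upper confidence limit for immediate minus postpartum ward has to fall below +12 h. The printed rule uses the other limit and the other side. For immediate minus ward, a lower limit above +12 h would demonstrate that immediate insertion delays lactogenesis by more than 12 h. For ward minus immediate, it would demonstrate that immediate insertion is more than 12 h faster. Neither is non-inferiority. The wording is valid only for ward minus immediate against a limit of −12 h, and the protocol states neither that order nor that sign.

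Because no other section supplies a rule, whoever analyses the trial has to reconstruct it. Two wrong reconstructions are possible. One adds a minus sign to the 12 but computes immediate minus ward, which guards against immediate insertion being too fast. The other takes the hypotheses at their word and treats a non-significant difference test as success. The trial is also unblinded, so the rule should be fixed in writing before any results are seen.

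**Working it through.** **Inputs.** From Number of subjects and statistical power: margin 12 h, one-sided alpha 5%, 80% power, true difference 0, SD 18 h (planning) and 12 h (cited), 68 patients, 82 recruited. No allocation ratio is given; Study Procedures says only "Participants will be randomized through block randomization". I assume 1:1, so 34 per arm, and a normal approximation. Let d be immediate minus ward, with SE = SD × √(2/n).

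**The plan's own figure.** n per arm = 2 × [18 × (1.645 + 0.842)/12]² = 27.8, rounded up to 28, so 56 in total. The stated 68 does not follow from the stated inputs. That is a separate matter; I use 68 below because it is the plan's number.

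**Standard errors.** SD 18: 18 × √(2/34) = 4.366. SD 12: 12 × √(2/34) = 2.910.

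**Thresholds for the observed difference.**
- Printed rule: lower limit above +12 means observed d > 12 + 1.645 × SE.
- Upper-limit rule: observed d < 12 − 1.645 × SE.
- Minus sign only: lower limit of d above −12 means observed d > −12 + 1.645 × SE.
- Non-significance (two-sided 5%): |observed d| < 1.96 × SE.

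| Rule | Quantity | SD 18 | SD 12 |
|---|---|---|---|
| Printed | Threshold (h) | 19.18 | 16.79 |
| Printed | P(success), true d = 0 | 0.0000056 | 0.000000004 |
| Upper limit < +12 | Threshold (h) | 4.82 | 7.21 |
| Upper limit < +12 | P(success), true d = 0 | 0.865 | 0.993 |
| Upper limit < +12 | P(success), true d = 12 | 0.05 | 0.05 |
| Minus sign only | P(success), true d = 12 | 0.99994 | > 0.99999 |
| Non-significance | Threshold (h) | 8.56 | 5.70 |
| Non-significance | P(success), true d = 12 | 0.215 | 0.015 |

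By symmetry, the printed rule has the same probability at d = 0 whichever way the difference is taken. At SD 18 it reaches 80% only if the true difference is 12 + (1.645 + 0.842) × 4.366 = 22.9 h. That contradicts the sentence's premise of no difference.

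**Where non-significance and non-inferiority disagree.** At SD 18, an observed delay of 4.82 to 8.56 h is non-significant but does not show non-inferiority. This occurs in 11% of trials with equal arms. At SD 12, an observed delay of 5.70 to 7.21 h is significant yet shows non-inferiority (1.8% of trials with equal arms).

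**Sensitivity.** With all 82 analysed (41 per arm), the non-significance rule passes a true 12 h delay 14% (SD 18) or 0.5% (SD 12) of the time. With an uneven 45:23 split at SD 18, the printed rule succeeds with probability 0.000011 at d = 0. At a true 12 h delay, the minus-sign-only rule passes 0.9998 of the time and the non-significance rule 0.26.

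**The case against.** The strongest reply is that the intent is clear. The margin is described as additional hours and justified by interventions that cause delay. The sentence also assumes no difference and expects 80% success, which excludes the literal reading. Only one coherent reading remains, and changing lower/above to upper/below is as easy as adding a minus sign. On this view the fault is one of notation, and no one would apply the printed rule.

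Much of that stands. The literal-rule probabilities show that the sentence contradicts itself; they do not forecast how the trial would be judged. The minus-sign and non-significance results describe hypothetical substitutes that the protocol does not adopt. At SD 12 the non-significance substitute is stricter than 5%, not looser. The looser hypothesis wording is a lesser point than the reversed limit, and rewording the expected-outcomes section is optional. The gap between 86.5% and the stated 80% reflects the sample-size arithmetic and is not evidence here.

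The reply does not remove the error. The sentence is the only statement of how the primary outcome will be judged, it is wrong under either order of subtraction, and the other sections point to a difference test. Having to recover the rule from context is itself a defect in a confirmatory criterion.

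**Conclusion.** The concern holds and should be corrected before analysis. The primary criterion is wrong as printed: under its own premise of equal arms it would be met about 6 times in a million at SD 18 h, and less often at SD 12 h, against the 80% claimed. Only the upper-limit form (or its mirror image, ward minus immediate against −12 h) fits the stated purpose, and it holds the error at a true 12 h delay to 5%. If the wording were repaired wrongly, a true 12 h delay could pass more than 99.99% of the time. If non-significance were used instead, the pass rate at the margin would range from 1.5% to 22% depending on the SD. These figures rest on a normal approximation and 34 per arm with 1:1 allocation, which the protocol does not state; the 45:23 check leaves the conclusions unchanged.

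**What to change.** Put the following in Data Analysis and make the sample-size paragraph agree with it:

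- Difference = mean time to lactogenesis stage II (immediate) minus mean time (postpartum ward).
- H0: difference ≥ 12 h. H1: difference < 12 h.
- Non-inferiority is concluded if the upper limit of the two-sided 90% confidence interval (equivalently, the one-sided 95% upper limit) is below +12 h.

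Restate the hypotheses in Project Summary, and the objective and hypothesis in Objectives and hypotheses, in terms of the 12-hour margin. Aligning the expected-outcomes section would help but is not essential. It is also worth saying that a non-significant difference test will not be taken as evidence of non-inferiority.

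The cost is a wording amendment. Margin, alpha, confidence level and sample-size formula do not change.
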